9.1.4.3. Analysis by Time After Infusion Start

IARs and anaphylactic reactions will be analyzed by the time after infusion start. Based on protocol descriptions of immediate-type IARs and late-type infusion reactions, the following time after infusion start will be used:

- 0 to < 2 hours, 2 to < 4 hours, 4 to < 6 hours, 6 to < 12 hours, 12 to < 24 hours (1 day), 1 to < 4 days (96 hours).

The event rates and changes in severity over time (over these intervals) will be summarized to help describe the clinical characteristics of IARs and anaphylactic reactions.

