13.1.3. Infusion-associated Reactions

An IAR is a disorder characterized by 1 or more adverse reaction(s) to the infusion of pharmacological or biological substances. These reactions are classified into 2 major subtypes, immediate and late, according to the time interval between the infusion and the onset of an infusion-related AE.

The reactions are divided into 5 severity grades as follows:

1. Mild (requires observation only); for example, transient flushing or rash
2. Moderate (minimal, usually oral, intervention suffices); for example, urticaria/myalgia/drug fever
3. Severe (vital organ involved yet not in a life-threatening manner; usually requires parenteral medication); for example, bronchospasm/angioedema/hypotension
4. Life threatening (multisystem involvement of vital organs, urgent and critical care required); for example, systemic anaphylactic reaction
5. Death

Immediate-type IARs commonly involve 1 or more of the following systems: skin (urticaria and erythema), eyes (conjunctivitis), nasopharynx (rhinorrhea, rhinitis), bronchopulmonary tissues (wheezing, bronchospasm), and gastrointestinal tract (diarrhea, vomiting).

Late-type reactions first manifest more than 24 hours postinfusion, usually 1 to 3 days postinfusion. The most common symptoms of late-type infusion reactions are pruritic skin eruptions, fever, malaise, and polyarthralgia.

Any symptom or sign occurring during or within 2 hours of completion of the infusion should be reported as an immediate-IAR and deemed drug-related AE, unless an alternative obvious explanation exists, eg, mechanical fall. Any symptom or sign occurring between 2 and 24 hours will be recorded as an IAR if it fits within the description of an IAR in the investigator's opinion. It would be reported as immediate-type IAR and deemed a drug-related AE.

Any symptom or sign occurring between 24 and 96 hours after completion of the infusion that, in the investigator's opinion, fits the clinical description of a symptom or sign associated with an IAR should be reported as a late-type IAR and deemed a drug-related AE.

A symptom or sign that occurs 24 hours or later and in the investigator's opinion is possibly, probably, or likely an IAR should be reported as such and deemed drug-related AE.

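### The SAP's IAR timing bins cite the protocol's immediate and late types but count from infusion start, so the 24 h and 96 h edges miss the protocol's limits and nothing is tabulated from 96 h on

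*SAP*

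**What the plan says.** SAP 9.1.4.3 breaks down IARs and anaphylactic reactions by time of onset. It gives the basis as "Based on protocol descriptions of immediate-type IARs and late-type infusion reactions" and the clock as "the following time after infusion start will be used". There are six half-open bins. The first four have edges at 0, 2, 4, 6 and 12 hours; the last two are "12 to < 24 hours (1 day), 1 to < 4 days (96 hours"), and no bin follows. SAP 9.1.3 uses the same intervals in the per-subject listing of infusions and IARs.

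Protocol 13.1.3 defines the types as follows:

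- **Immediate, first window:** "Any symptom or sign occurring during or within 2 hours of completion of the infusion should be reported as an immediate-IAR", unless there is an obvious alternative explanation.
- **Immediate, second window:** "Any symptom or sign occurring between 2 and 24 hours will be recorded as an IAR" if the investigator judges that it fits the description, and "It would be reported as immediate-type IAR and deemed a drug-related AE".
- **Late:** "Any symptom or sign occurring between 24 and 96 hours after completion of the infusion", again if it fits clinically. The general description is "Late-type reactions first manifest more than 24 hours postinfusion, usually 1 to 3 days postinfusion".

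A further sentence in the same section lets the investigator report as an IAR anything judged to be one from 24 hours onward, with no upper limit.

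The infusion is planned at about 4 hours (Protocol 10, Table 8, and 11.5.1). The frequency and severity of immediate and late IARs is a safety endpoint in both documents (Protocol 15.1.5; SAP 3.3.6).

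**The concern.** Because the SAP ties its bins to the protocol types, a reader will take the 24 h edge as the divide between immediate and late and the 96 h edge as the end of the late window. Those readings are right only if the infusion takes no time.

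This matters because SAP 9.1.4.3 is the only analysis section of the SAP that names the two types, and no other section gives a rule for tabulating them. SAP 9.1.3 describes the eCRF entry as whether the event is an IAR and how it relates to each drug component; it mentions no immediate/late field. Someone assembling the immediate/late endpoint from the planned outputs would therefore turn to these bins. At stake is whether those outputs can show the stated endpoint.

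**Working it through.** **Inputs**

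- Protocol limits after completion: 2, 24 and 96 h (Protocol 13.1.3).
- Planned infusion duration T: about 4 h (Protocol 11.5.1).
- SAP bin edges after start: 0, 2, 4, 6, 12, 24 and 96 h (SAP 9.1.4.3).

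**Origin of the 24 h limit.** The sentence on the 2 to 24 hour window does not restate its origin. The sentences before and after it count from completion, and the general description of late reactions is worded as postinfusion. Completion is the natural reading, though an inferred one.

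**Conversion.** Hours after start = hours after completion + T. With T = 4:

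| Protocol limit (after completion) | After start | SAP edge | Match |
|---|---|---|---|
| 2 h | 2 + 4 = 6 h | 6 h | yes |
| 24 h | 24 + 4 = 28 h | 24 h | no |
| 96 h | 96 + 4 = 100 h | 96 h | no |

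The SAP's 24 h and 96 h edges equal the protocol limits only when T = 0.

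**Consequences at T = 4**

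- Onsets 24 to 28 h after start are 20 to 24 h after completion. They lie in the protocol's immediate window but enter the bin from 1 to under 4 days. That is 4 of the 24 post-completion hours, 4/24 = 17%.
- Onsets 96 to 100 h after start are 92 to 96 h after completion. They lie in the late window but have no bin. That is 4 of the 72 late hours (96 − 24), 4/72 = 5.6%.
- An IAR reported beyond that point also has no bin, although the protocol allows one.
- The last bin is open at its upper end, so an onset at exactly 96 h has no bin even if T = 0.

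The percentages are shares of clock time, not of events. The documents give no distribution of onset times.

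**Other durations.** The displaced stretch has length T at each of the two edges. Taking T = 3 h or 6 h as assumptions, the stretches are 24 to 27 h and 96 to 99 h, or 24 to 30 h and 96 to 102 h. The agreement at 6 h then also fails, because completion + 2 h becomes 5 h or 8 h.

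**The case against.** The strongest reply is that no event changes type. SAP 9.1.4.3 labels no bin immediate or late and gives no rule deriving type from the bins. Its heading announces time after infusion start, and its six intervals are finer than the two types. Under Protocol 13.1.3 the investigator assigns the type when reporting. That stands. A reader might infer that reactions will be misclassified, but the documents do not support this: a display bin cannot alter a reported type, and the overall IAR tables of SAP 9.1.3 do not depend on the bins.

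The bins also partly allow for the infusion. At 4 hours, the first two cover the infusion itself and the third covers the first 2 hours after it. That stands as well, and limits the mismatch to the 24 h and 96 h edges.

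A reader might further infer that the error is largest in subjects who react, because Protocol Table 14 halves the rate for a mild reaction. The documents do not show this. Slowing follows the reaction that triggers it, so that reaction's time from start is unchanged; only a separate, later event could be affected. Table 14 also allows a return to the previous rate, and after a severe reaction any re-initiation is at the 4-hour duration. It gives no prolonged total duration from which to size a larger shift.

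Finally, the remedy has its own difficulty. Table 14 allows an infusion to be suspended and restarted 48 hours later, or re-initiated after 7 to 14 days, so the end of an infusion is not always a single moment. This does not defend the present bins, but the fix must deal with it.

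**Conclusion.** The point holds as a minor inconsistency. The SAP claims a basis in the protocol types and uses a different time origin. At the nominal duration, two 4-hour stretches are affected: one inside the immediate window is tabulated with later onsets, and one inside the late window is not tabulated. Later IARs are also left out, whichever origin is used.

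This rests on a 4-hour infusion and on reading the protocol's 24 h limit as counted from completion. The missing final bin rests on neither. How many events are involved cannot be said from the documents. Protocol 13.1.3 puts late reactions usually at 1 to 3 days, so the stretch near 96 h is outside the usual range.

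The effect is confined to the timing tables for IARs and anaphylactic reactions and to the per-subject listing. Safety is summarised without formal tests (SAP 9), so no inferential result depends on it.

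**What to change.** In SAP 9.1.4.3:

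1. Add a tabulation by time from infusion completion for the immediate/late endpoint: during infusion, 0 to 2 h, >2 to 24 h, >24 to 96 h, and >96 h.
2. Keep the from-start bins as a separate display, add a final bin for 96 h and later, and remove the statement that they are based on the protocol types.
3. State how onset is timed when an infusion is interrupted or re-initiated, including which start and which completion apply.
4. Carry the same intervals into the per-subject listing in SAP 9.1.3.

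The cost is SAP wording and modest programming. Event start times are collected (Protocol 13.2), and changes in infusion duration are documented in the eCRF (Protocol 12.2.3). The documents do not say that an infusion end time is captured, so the sponsor should confirm this first. No change to trial conduct is needed if it is.

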9.1.5. Describing Relationship to Study Drug

For each AE entered on the AE eCRF, the reporting investigator was asked to assess relationship to both infusion drug (ATB200 or alglucosidase alfa) and capsule (AT2221 or placebo). The relationship to each study drug will be presented by 2 categories:

- “related,” which includes possibly related, probably related, and definitely related, as reported by the investigator
- “not-related,” which includes unrelated and unlikely related, as reported by the investigator

To describe the overall relationship to study drug, two approaches will be presented:

1. Based on the pooling into one designation of the two individual relationships to ATB200 or alglucosidase alfa and AT2221 or placebo
 - a. If the two categories of the individual relationships are discordant (ie, “related” to one and “not related” to the other), the pooled designation will be considered “related”
 - b. If the two categories of the individual relationships are concordant (ie, “related” to both or “not related” to both), the pooled designation will be concordant with the individual categories
2. Based on the assessment of causality to the individual component, yielding these possible combinations
 - a. “Related” to ATB200 – “related” to AT2221
 - b. “Related” to ATB200 – “not related” to AT2221
 - c. “Not related” to ATB200 – “related” to AT2221
 - d. “Not related” to ATB200 – “not related” to AT2221
 - e. “Related” to alglucosidase alfa – “related” to placebo
 - f. “Related” to alglucosidase alfa – “not related” to placebo
 - g. “Not related” to alglucosidase alfa – “related” to placebo
 - h. “Not related” to alglucosidase alfa – “not related” to placebo

9.1.6. Missing AE Onset Date, Severity, and Relationship

9.1.6.1. Missing or Partial AE Onset or Medication Start Date

Complete dates are very important to correctly describe safety events such as TEAEs and designation of unique AE occurrences. When dates are completely missing or partially missing, they will be imputed.

The following algorithm will be used to impute partial or missing AE start dates:

1. If Year is not missing and is after the year of first application of study drug:
 - If Month is missing, then Month will be imputed as January.
 - If Day is missing, then Day will be imputed as the first of the month.
2. If Year is not missing and is the same as the year of the first application of study drug:
 - If Month is missing, then impute the Month as the month of the first application of study drug.
 - If Day is missing but Month is the same as the month of first application of study drug, then impute Day as the first day of study drug application.
 - If Day is missing but Month is after the month of first application of study drug, then impute Day as the first of the month.
3. If Year is missing, then impute the year as the year of the first application of study drug:
 - If Month is missing, then impute the Month as the month of the first application of study drug.
 - If Day is missing, then impute the Day as the day of the first application of study drug.
4. If the start date is completely missing, but the AE is either ongoing or the stop date is after the first date of drug application, then impute the start date as the first application of study drug.
5. If using the above rules, the stop date is before the start date, then leave the start date missing and assume that the AE is treatment-emergent for the purpose of the analysis.

No imputations will be applied to AE stop dates.

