12.3.8. Adverse Events

Reporting of AEs begins after written informed consent is provided, including study-related events that occur as a direct result of a study procedure (eg, if a subject falls during a functional assessment) and IARs. As required by their institutions, investigators will be responsible for reporting AE information to their IRB, IEC, or REB (see Section 13). If the start date of an AE is prior to enrollment in this study, it should be captured as medical history.

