6.4.1. Missing AE Attributes

Adverse events with missing attributes will be imputed with the worst possible outcome, for summary purposes. For example, if an AE is missing relationship to study drug, it will be imputed as being ‘related’ to the study drug; if an AE is missing the severity level, it will be imputed as being ‘severe.’

Nonetheless, in the data listings, the actual observed values will be reported. That is, if the response is missing, it will show as missing in the data listings.

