9.1. Treatment-emergent Adverse Events

Summary of adverse events will be based on TEAEs. A TEAE is defined as any event that started or changed in the severity on or after the first dose of study drug.

For AEs occurring on Day 1, if the start time of the event is missing or after the administration of the first dose of study drug, the event will be considered a TEAE.

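### The SAP's adverse event start-date rules have no floor at first dose, so an on-treatment event with an unknown year or month can be imputed to a pre-dose date and leave the TEAE tables

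*SAP*

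**What the plan says.** SAP Section 6.4.3 sends missing adverse event dates to Section 9.1.6, where 9.1.6.1 gives five rules for start dates.

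- Rule 1 covers a known year later than the first-dose year. A missing month becomes January and a missing day the first of the month.
- Rule 2 begins "If Year is not missing and is the same as the year of the first application of study drug". Under it, "If Month is missing, then impute the Month as the month of the first application of study drug". Its day instructions apply only when the day is missing.
- Rule 3 says "If Year is missing, then impute the year as the year of the first application of study drug". A missing month or day is then also taken from the first dose.
- Rule 4 applies "If the start date is completely missing, but the AE is either ongoing or the stop date is after the first date of drug application"; the start then becomes the first-dose date.
- Rule 5 acts only where an imputed start would fall after the recorded end of the event. The start then stays blank and the event counts as a TEAE.

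SAP Section 9.1 states "Summary of adverse events will be based on TEAEs". It defines a TEAE by an onset, or a change in severity, at or after first dosing. SAP Section 6.4.1 states "Adverse events with missing attributes will be imputed with the worst possible outcome, for summary purposes", with relationship and severity as its examples. Protocol Section 12.3.8 starts adverse event reporting at consent and adds "If the start date of an AE is prior to enrollment in this study, it should be captured as medical history".

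**The concern.** Treatment lasts 52 weeks, so for nearly every subject it crosses a calendar year-end. If the year of onset is unknown, rule 3 always chooses the first-dose year, even where a known month points to the following year. With first dose on 15 November 2019, an event recorded as 12 March of an unknown year becomes 12 March 2019, eight months before dosing. Planned screening is at most 30 days and earlier onsets belong in medical history, so March 2020 is the natural reading.

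Rule 2 has a milder form of the fault. With first dose on 15 June 2019, day 5 of an unknown month in 2019 becomes 5 June 2019.

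An event dated this way is classed as pre-treatment. It drops out of the overall TEAE summary and the tables of serious, related and discontinuation events built on it. The error runs towards under-counting harm.

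**Working it through.** The plan states no figure for this, so there is none to reproduce. The check applies the rules literally.

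**1. Single records.** First dose 20 September 2019:

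| True onset | Parts recorded | Rule | Imputed start |
|---|---|---|---|
| 14 Feb 2020 | day, month | 3 | 14 Feb 2019 |
| 14 Feb 2020 | month | 3 | 20 Feb 2019 |
| 5 Nov 2019 | day, year | 2 | 5 Sep 2019 |
| 5 Nov 2019 | day | 3 | 5 Sep 2019 |

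All four fall before first dose. By contrast, day 5 of an unknown month in 2020 becomes 5 January 2020 under rule 1, which is after first dose. Rule 3 can also give a non-existent date: with first dose on the 31st of a month and only April known, it returns 31 April.

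**2. Can rules 4 or 5 catch these?** Rule 4 needs a completely missing start date, so a partial date never reaches it. Rule 5 needs a stop date before the imputed start. For a back-dated on-treatment event, stop ≥ true onset ≥ first dose > imputed start, so that condition cannot be met. Section 6.4.3 only refers back to 9.1.6, and the Day 1 provision in 9.1 concerns missing times.

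**3. How often, given such a record?** Assumption, not in the documents: first doses are spread evenly over the calendar year.

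*Year missing, month and day known.* Within 52 weeks, the event is back-dated exactly when the true onset falls in the next calendar year. An onset k days after first dose does so with probability k/365, so the share is (mean k)/365.

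- Onsets even over 52 weeks (mean k = 182): 182/365 = 49.9%.
- Onsets even over the first 90 days (mean k about 45): 45/365 = 12%.

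*Month missing, day and year known.* Only onsets in the first-dose year are at risk. With even onset over 52 weeks that is 100% − 49.9% = 50.1% of them. Of these, 43.8% are back-dated on enumeration, so 50.1% × 43.8% = 22%. Earlier onset moves this figure the other way: with the 90-day pattern about 88% fall in the first-dose year, and 88% × 43.8% is about 39%.

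Enumerating every first-dose day in a year against every onset day, with day numbers cut to the length of the month, gives the share of on-treatment onsets placed before first dose:

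| Missing | 52 weeks | 52 weeks + 30 days |
|---|---|---|
| Year | 49.9% | 46.6% |
| Year and day | 46.1% | 42.8% |
| Year and month | 48.2% | 48.1% |
| Month | 22.0% | 20.3% |
| Day | 0% | 0% |
| Month and day | 0% | 0% |
| All, event ongoing or stopped after first dose | 0% | 0% |

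Without the cut to month length, about 0.2% to 1.7% of records in the affected patterns become impossible dates.

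**4. After the proposed change.** For a true onset between first dose and last dose + 30 days, the true date itself agrees with the known parts and is no later than the stop date. A qualifying date therefore always exists, and the share placed before first dose is 0% in every pattern.

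**The case against.** The case for leaving the rules alone has real force.

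- **Rarity.** A larger date part must be missing while a smaller one is known. Protocol Section 13.2 requires start and end date and time for each event, Table 10 collects events at every two-weekly infusion visit, and Section 14 provides for cleaning of inconsistencies. Serious events are due within 24 hours (Section 13.3), so one with an unknown year is hard to picture. This stands.
- **Not lost from view.** SAP Section 9.1.2 lists all adverse events, with separate listings for deaths and serious events. An event whose severity changed on or after first dose remains a TEAE. An infusion-associated reaction dated before any infusion contradicts itself and should be queried. This stands.
- **Some imputed dates are plausible.** A missing-month imputation stays within the first-dose month, so the date may be a genuine screening onset. The percentages above describe only events that truly began on treatment.
- **Limited inferential reach.** The rules are the same in both arms, and SAP Section 9 plans no formal safety tests.

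A reader might infer that such events vanish from every safety output, that half of all partially dated events are lost, or that the arms are affected differently. The documents support none of these: the listing remains, the usual patterns give 0%, one in two depends on an assumed onset pattern, and nothing points to a difference between arms. A reader might also see a direct contradiction with Section 6.4.1. Its examples are relationship and severity, and dates are sent elsewhere, so the rules are out of keeping with that principle rather than in conflict with it.

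None of this makes the rule correct. A record with a known month can be dropped while a completely undated ongoing event is counted, which is unlikely to be intended.

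**Conclusion.** The point holds in a limited form. Rules 2 and 3 can place an on-treatment event before first dose, or on an invalid date, when the year is missing with the month or day known, or when the month is missing with the day known in the first-dose year. This is a wrong rule, not missing detail, because following it as written misclassifies the event. The effect is on the TEAE-based summaries, for events without a severity change on or after first dose.

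The expected number is probably small and cannot be estimated from the documents. The conditional chances rest on an even spread of first doses and an assumed onset pattern: about 12% to 50% for a missing year, and about 22% for a missing month under even onset over 52 weeks (higher if onsets are early). SAP Section 9.4.1 reuses the rules for medication start dates. The consequence there is smaller, because Section 7.8 already counts a medication that stops after first dose as concomitant.

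**What to change.** Add to SAP Section 9.1.6.1:

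> If the date obtained under rules 2 or 3 is before the first dose or is not a valid date, and the known date parts, consent date and stop date do not show that the AE began before first dose, impute the earliest valid date that agrees with the known parts, is on or after first dose, and is no later than the AE stop date and last dose + 30 days. If no such date exists and the known parts fit a date between consent and first dose, keep that date as pre-treatment. Otherwise leave the start date missing and treat the AE as treatment-emergent, as in rule 5. If the known parts fit both a date between consent and first dose and a date on treatment, treat the AE as treatment-emergent for summaries and flag it in the listing.

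The upper bound matters. With first dose on 15 November 2019 and an ongoing event on 10 November of an unknown year, rolling forward without a limit gives 10 November 2020. For an early withdrawal that lies beyond last dose + 30 days, where Section 9.1.1 would drop the event, and it may move a true screening event forward by a year.

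The cost is one short paragraph and a few lines of code before database lock. The downside is that a few uncertain pre-dose events may be counted as treatment-emergent, in line with the SAP's conservative handling of missing severity and relationship.

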7.8. Prior and Concomitant Medications and Nondrug Therapies

Prior medications and nondrug therapies are defined as any medication or nondrug therapy taken or occurring before the first dose of study drug. Concomitant medications and nondrug therapies include medications and nondrug therapies with start dates (and times) on or after the first dose of study drug, medications and nondrug therapies with onset dates (and times) prior to the first dose of study drug without a stop date, or medications and nondrug therapies with a stop date (time) after the first dose of study drug. Medications starting after the last dose of study drug will not be considered as concomitant but will be flagged as post medications in the listing of medications. Nondrug therapies include physiotherapy and occupational therapy, procedures, surgery, or use of assistive devices.

Prior and concomitant medications are coded to indication-specific Anatomical Therapeutic Chemical classification (ATC) and preferred name using the World Health Organization Drug Dictionary (WHO DDE, September 2013 or later).

Prior and concomitant medication use will be summarized by level 4 ATC and preferred name using the number and percentage of subjects by treatment group. Medications will be sorted alphabetically by ATC and preferred name within ATC, and in decreasing order of the total number of subjects who took each medication within each ATC class. Subjects with multiple occurrences of a medication in ATC and preferred name will only be counted once within each ATC and preferred name. In addition, the total number of subjects to ever take any concomitant medications will be presented. Since medications are coded to ATC by indication, preferred names may appear under multiple ATCs.

A listing of all medications, both prior to infusions and concomitant, and nondrug therapies will be presented. Investigator verbatim descriptions as well as coded terms will be included in the listings. Any abbreviations and codes will be clearly explained on each page of the listing. The listing will be sorted by treatment group and subject identifier, and will include level 4 ATC,

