9.1.6.2. Missing or Partial Medication Stop Date

References to year and month are the year and month of the stop date:

1. If year and month are known and study medication stopped during that month and year, use the stop date of study medication.
2. If year and month are known and informed consent was provided during that month and year, use the date of informed consent.
3. If year and month are known and study medication stopped after the date of informed consent and not in the month that medication stopped, use the last day of the month.

4. If year and month are known and are prior to the month of informed consent, use the first day of the month.
5. If only year is known and study medication stopped during that year, use the stop date of study medication.
6. If only year is known and study medication stopped after that year, use December 31st of that year.
7. If only year is known and study medication stopped prior to that year, use the first day of the year.
8. Should any of the previous stop dates be created before a start date, either a complete date or an imputed one, use the (imputed) start date instead of the date that would otherwise be created.
9. Otherwise, if stop date is unknown, leave as missing.

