9.4. Duration of Therapy and Missing Medication Start and Stop Dates

9.4.1. Missing and Partial Concomitant and Other Medication Start and Stop Dates

Incomplete concomitant medication start dates will be imputed in the same manner as imputation of AE start dates described in Section 9.1.6.1. No imputations will be applied to the medication stop date. If, when using those rules, the stop date is before the start date, then the start date will be left as missing and it will be assumed that the medication is concomitant for the purpose of the analysis. Imputed dates will be flagged in the subject data listings.

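### SAP 9.1.6.1 rule 5, copied for medicines in 9.4.1, counts some records that ended before the first dose as treatment-emergent or concomitant

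*SAP*

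**What the plan says.** SAP 9.1.6.1 gives five rules for partial or missing AE start dates. When the year is that of the first dose, a missing month takes the first-dose month. For a missing day in the first-dose month the instruction is "then impute Day as the first day of study drug application". Rule 3 fills a missing year, month or day from the first-dose date. Rule 4 applies "If the start date is completely missing, but the AE is either ongoing or the stop date is after the first date of drug application" and imputes the first-dose date. Rule 5 covers a conflict left by the earlier rules: if "the stop date is before the start date, then leave the start date missing and assume that the AE is treatment-emergent". AE stop dates are not imputed.

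SAP 9.4.1 applies the same start-date algorithm to medicines. Where the stop falls before the start, "then the start date will be left as missing and it will be assumed that the medication is concomitant".

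The definitions are elsewhere. SAP 9.1: "A TEAE is defined as any event that started or changed in the severity on or after the first dose of study drug". SAP 7.8 counts a medicine as concomitant if it started on or after first dose, if it started earlier and has no stop date, "or medications and nondrug therapies with a stop date (time) after the first dose of study drug".

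On medication stop dates, SAP 9.1.6.2 lists nine rules, beginning "If year and month are known and study medication stopped during that month and year, use the stop date of study medication". SAP 9.4.1 says "No imputations will be applied to the medication stop date".

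**The concern.** Rule 5 treats a stop date that precedes the imputed start as an unresolvable conflict and settles it by a worst-case assumption. In the common partial-date patterns the conflict is not unresolvable. It arises only because the imputed start was placed at first dose while the event had already ended, so the recorded stop date answers the question that the rule goes on to assume the other way.

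At stake are the TEAE tables and the concomitant-medication tables, which would include some events and medicines that the SAP's own definitions place before treatment. A programmer following the text exactly would produce that result. One who noticed the problem would have to depart from the SAP.

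**Working it through.** No power or alpha calculation is involved. The check is to trace each branch and compare the outcome with the definitions.

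**Step 1. What each branch of SAP 9.1.6.1 imputes**

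| Known part of start date | Rule | Imputed start | Can a valid recorded stop precede it? |
|---|---|---|---|
| Year after first-dose year | 1 | Earliest date in the known period | No |
| First-dose year, later month, day missing | 2 | First of that month | No |
| First-dose year and month, day missing | 2 | First-dose date | Only if the stop is before first dose |
| First-dose year, month and day missing | 2 | First-dose date | Only if the stop is before first dose |
| Nothing known | 3, or 4 if that is read as governing | First-dose date | Under rule 3, only if the stop is before first dose; under rule 4, no |
| Day known with month missing, or year missing with month or day known | 2 or 3 | Known parts kept, the rest from first dose | Yes, with the stop on either side of first dose |
| Year, or month within the first-dose year, known to precede first dose (later parts missing) | None | Not imputed | Rule 5 is not reached |

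**Step 2. Consequence for the rows imputed to first dose.** The AE stop date is as recorded. If stop < imputed start, and imputed start = first dose, then stop < first dose. The true start cannot be later than the stop, so the event began and ended before dosing. It could neither start nor change in severity on or after first dose. It fails SAP 9.1 and also Protocol 13.1.1, which requires onset after the first dose. A medicine with the same dates meets none of the three limbs in SAP 7.8 and is prior only.

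**Step 3. Dates put in (assumed, for illustration)**

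- First dose 15 June 2019, start June 2019 with day missing, stop 10 June 2019. Imputed start 15 June; the stop is earlier; 15 − 10 = 5 days before dosing. Rule 5 gives treatment-emergent for an AE, and 9.4.1 gives concomitant for a medicine. Both are wrong.
- First dose 20 March 2019, start 2019 with month and day missing, stop 5 March 2019. Imputed start 20 March; 20 − 5 = 15 days before dosing. Same result.
- First dose 20 March 2019, medicine start on day 28 of an unknown month in 2019, stop 22 March 2019. Imputed start 28 March; the stop is earlier, so the medicine is called concomitant. The stop is after first dose (22 > 20), so here the answer is right.

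**Step 4. Grid check.** The five rules were run over three assumed first-dose dates, true starts from 60 days before to about a year after first dose, and durations of 0 to 120 days.

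- Usual patterns (day missing; month and day missing; all missing): rule 5 fired 274 times through rule 2 and 309 times through rule 3, 274 + 309 = 583. In all 583 the stop was before first dose. If rule 4 governs wholly missing starts, the 274 remain, again all pre-dose.
- Unusual patterns (sixth row of the table): 495 + 184 = 679 firings had a stop before first dose, and 97 + 358 + 25 = 480 had a stop on or after it.
- In the usual patterns, 160 + 184 = 344 records that ended before dosing had a start year or month known to precede first dose, and rule 5 did not reach them.

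These counts show the logic only. They do not estimate frequency in the trial.

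**Step 5. Medication stop dates.** SAP 6.4.2 sends the reader to 9.4.1 for start and stop dates, and 9.4.1 imputes no stop dates. SAP 9.1.6.2 imputes them under nine rules. The two also resolve a stop-before-start conflict differently: rule 8 of 9.1.6.2 moves a created stop date to the start, while 9.4.1 blanks the start. Both cannot be programmed.

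**The case against.** The strongest reply is that the rule is conservative and its reach is narrow. It treats both arms alike, errs towards over-counting, and fits the worst-case handling of missing AE attributes in SAP 6.4.1. Safety summaries carry no formal tests (SAP 9), and the AE listing shows onset and resolution dates (SAP 9.1.2), so a pre-dose stop could be seen. Protocol 13.2 requires the date and time of start and end for each AE, screening lasts up to 30 days (Protocol 8.2), and events that began before enrolment go to medical history (Protocol 12.3.8). All of this stands as a limit on size. It does not rescue the rule: worst-case imputation is for facts that are unknown, and here the recorded stop date settles the timing.

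Three stronger readings are tempting, and the documents do not support them.

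- A reader might infer that every record caught by rule 5 is misclassified. Known date parts are kept, so rule 5 can also fire with a stop on or after first dose, where the default is acceptable (third example above).
- A reader might infer that the medication history of about 2 years (Protocol 12.3.3) makes the error common. Most of that inference fails, because starts known to lie in a year or month before first dose have no imputation rule.
- A reader might infer that pre-dose events will be reported as severe and drug-related through SAP 9.1.6.3 and 9.1.6.4. That needs severity and causality to be missing on the same record as well, and nothing suggests that this will happen.

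Nor is rule 4 strictly contradicted. It has a different trigger, a completely missing start. Its condition does show that the authors meant the first-dose default for events that were ongoing or ended later.

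**Conclusion.** The concern holds for a defined set of records: those whose start date is imputed to the first-dose date and whose recorded stop date is before first dose. The start patterns are day missing in the first-dose month; month and day missing in the first-dose year; and all parts missing, unless rule 4 is read as governing. For these, SAP 9.1.6.1 rule 5 and SAP 9.4.1 give a classification opposite to SAP 9.1 and 7.8. This is a stated rule with a wrong result, not a missing detail.

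The number of affected records cannot be derived from the documents and is probably small. The effect is confined to descriptive safety and medication summaries; efficacy analyses are untouched. The conclusion assumes that recorded stop dates are correct and that the rules are applied as written. The conflict between 9.1.6.2 and 9.4.1 on medication stop dates is a separate, plain inconsistency. It is worth correcting both before database lock.

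**What to change.** - **SAP 9.1.6.1, rule 5.** If the recorded stop date, or its known parts, places the end of the event before the first dose, leave the start date missing and classify the AE as not treatment-emergent. Keep the treatment-emergent default only when the stop date is missing, cannot be placed before first dose, or is on or after first dose.
- **SAP 9.4.1.** Make the same change: a medicine whose stop is before first dose is prior only, and the concomitant default stays for the other cases.
- **Rules 3 and 4.** State which governs a completely missing start date.
- **Medication stop dates.** Keep either 9.1.6.2 or the no-imputation sentence in 9.4.1, and align 6.4.2 with the choice. If 9.1.6.2 is kept, its rule 8 needs the same pre-dose condition. Otherwise an imputed stop that is known to precede first dose could be moved to a start imputed at first dose.

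The cost is a few sentences of SAP text and one added condition in each of the AE and medication date derivations. No data collection or efficacy analysis changes.
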